4.6 General Concomitant Medication and Supportive Care Guidelines

In the rare event that a patient is taking an anti-neoplastic therapy (chemotherapy, targeted therapy) for any reason (immune disease, malignancy), said medication must be withheld at least 7 days prior to and 7 days after delivery of SBRT.

All other standard concomitant medications deemed necessary for management of the patient’s arrhythmia and overall health should be continued, and need not be altered for purposes of SBRT delivery.

Though not yet seen in our preliminary experience, given the proximity of the esophagus and stomach to the heart, it is possible that patients may develop esophagitis or gastritis. Treatment of esophagitis/gastritis varies with the severity of the patient’s symptoms; for example, diet adjustment and narcotic management may be sufficient for grade 2 complications. Nutritional support via gastric tube or jejunostomy tube may be initiated upon development of grade 3-4 complications, per mutual preference of the treating physician and patient.

4.7 Women of Childbearing Potential

Women of childbearing potential (women with regular menses, women with amenorrhea, women with irregular cycles, women using a contraceptive method that precludes withdrawal bleeding, and women who have had a tubal ligation) are required to have a negative pregnancy test within 14 days prior to the start of SBRT.

If a patient is suspected to be pregnant, SBRT should not be administered. In addition a positive urine test must be confirmed by a serum pregnancy test. If it is confirmed that the patient is not pregnant, the patient may resume therapy.

4.8 Duration of Therapy

Because this study involves administration of a single fraction of SBRT over the course of approximately 10 minutes, there is no option for discontinuation of treatment once initiated.

4.9 Duration of Follow up

Patients will be followed per protocol for 12 months following the completion of SBRT or until death, whichever occurs first. Follow-up is per the treatment calendar (see Section 8.0) and consists of routine clinical visits, 12-lead EKG and implanted device interrogations to evaluate toxicity and treatment response, and evaluation of QOL. Patients will be followed by office visits, phone calls, and review of medical record. Any additional follow-up and imaging will be obtained off-study as per routine clinical policies of the treating physician. After 12 months, patients will be followed at the discretion of the treating physicians. Patients will be tracked for clinical outcomes up to 5 years after completion of radiation via review of the medical record.

4.10 Management of ICD Programming and Antiarrhythmic Medications During Follow up

ICD programming parameters and antiarrhythmic medication dosing should be patient-specific decisions, left to the treating physician taking into account risks and benefits of the various strategies. Ideal settings are suggested below:

- ICD programming should include a zone for detection at least 20ms slower than the slowest clinical or induced VT. ICD therapy may or may not be programmed to deliver therapy in this zone, subject to decisions about patient symptoms and tolerances during VT.
- Antiarrhythmic medications should be maintained at pre-treatment doses for at least the first 6 weeks, barring any development of adverse medication effect.
- With each subsequent visit after the first 6 weeks, doses of at least one antiarrhythmic medication should be reduced if no VT has been observed on ICD device check.

- If not contraindicated, oral anticoagulation is preferred during the first month after treatment (warfarin, dabigatran, rivaroxaban, apixaban or edoxaban) to minimize risks of stroke.

5.0 REGULATORY AND REPORTING REQUIREMENTS

5.1 Adverse Events (AEs)

Definition: any unfavorable medical occurrence in a human subject including any abnormal sign, symptom, or disease.

Grading: the descriptions and grading scales found in the revised NCI Common Terminology Criteria for Adverse Events (CTCAE) version 4.0 will be utilized for all toxicity reporting. A copy of the CTCAE version 4.0 can be downloaded from the CTEP website.

Advancing heart failure symptoms will be monitored closely, and represent a difficult endpoint to assess objectively. It is acknowledged that heart failure progression is an expected natural history irrespective of cardiac ablation. Inotrope or mechanical support may become necessary, and if used, specific scoring criteria will be used to adjudicate treatment-related HF progression vs. natural history of HF. For the purposes of this study, which studies the short-term toxicities of the therapy, treatment-related adverse heart failure event will be defined as either:

- 1) Acute worsening of heart failure symptoms requiring initiation of new IV vasoactive medications (inotropes or vasopressors) within the first six weeks of treatment;
- 2) Acute reduction in left ventricular ejection fraction (>10% reduction) within the first six weeks of treatment

We recognize that because of the relatively slow-acting nature of radiotherapy, potential treatment-related heart failure progression fall outside the six-week window defined above. Long-term clinical care and observation will be important, but are outside the scope of this project. For best patient care, decisions regarding heart transplant status and candidacy for inotrope or mechanical support will not be affected by enrollment in this study.

Attribution (relatedness), Expectedness, and Seriousness: the definitions for the terms listed that should be used are those provided by the Department of Health and Human Services' Office for Human Research Protections (OHRP). A copy of this guidance can be found on OHRP's website:

<http://www.hhs.gov/ohrp/policy/advevntguid.html>

5.2 Serious Adverse Events (SAEs)

Definition: An adverse event that is any undesirable experience associated with the use of a medical product in a patient that results in death, hospitalization (new or prolonged), disability or permanent damage, or is life-threatening.

Specific to this protocol, SAEs are defined as AEs with CTCAE v4.0 grade 3 or higher resulting in hospitalization or grade 4-5 AE. Treatment-related SAEs were SAEs that are possibly, probably, or definitely related to protocol treatment.

5.3 Unanticipated Problems

Definition:

- Unexpected (in terms of nature, severity, or frequency) given (a) the research procedures that are described in the protocol-related documents, such as the IRB-approved research protocol and informed consent document; and (b) the characteristics of the subject population being studied;
- Related or possibly related to participation in the research (“possibly related” means there is a reasonable possibility that the incident, experience, or outcome may have been caused by the procedures involved in the research); and
- Suggests that the research places subjects or others at a greater risk of harm (including physical, psychological, economic, or social harm) than was previously known or recognized.

5.4 Noncompliance

Definition: failure to follow any applicable regulation or institutional policies that govern human subjects research or failure to follow the determinations of the IRB. Noncompliance may occur due to lack of knowledge or due to deliberate choice to ignore regulations, institutional policies, or determinations of the IRB

5.5 Serious Noncompliance

Definition: noncompliance that materially increases risks, that results in substantial harm

5.6 Protocol Exceptions

Definition: A planned deviation from the approved protocol that are under the research team’s control. Exceptions apply only to a single participant or a singular situation.

Pre-approval of all protocol exceptions must be obtained prior to the event.

5.7 Reporting to the Human Research Protection Office (HRPO) at Washington University

The PI is required to promptly notify the IRB of the following events:

- Any unanticipated problems involving risks to participants or others which occur at WU, any BJH or SLCH institution, or that impacts participants or the conduct of the study.
- Noncompliance with federal regulations or the requirements or determinations of the IRB.
- Receipt of new information that may impact the willingness of participants to participate or continue participation in the research study.

These events must be reported to the IRB within **10 working days** of the occurrence of the event or notification to the PI of the event. The death of a research participant that qualifies as a reportable event should be reported within **1 working day** of the occurrence of the event or notification to the PI of the event

5.8 Timeframe for Reporting Required Events

Adverse events captured in the CRFs will be tracked for 12 months following SBRT. For the purposes of this protocol, reportable adverse events are grade 3, 4, or 5 toxicities that did not predate SBRT and are possibly, probably or definitely attributable to treatment. Patients will be assessed using the CTCAE v4.0.

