2.0 OBJECTIVES

2.1 Primary Objectives

1. Phase I - Demonstrate acute (≤ 90 days) safety of noninvasive stereotactic cardiac ablation radiotherapy (ENCORE). The **primary safety endpoint** is defined by a $\leq 20\%$ rate of serious adverse events (SAEs) using CTCAE v4.0 criteria that are possibly/probably/definitely related to study treatment, based on previously published data for expected invasive catheter-based VT-ablation procedures.
2. Phase II - Demonstrate preliminary efficacy of ENCORE. The **primary efficacy endpoint** is defined by the number of subjects with a reduction in ICD therapies (ATP and ICD shocks) comparing the period six months before ENCORE treatment to the six months after ENCORE treatment as adjudicated by continuous ICD monitoring. There will be a six-week “blanking period” after therapy to allow for ablation effect. For patients with PVC-induced cardiomyopathy, the primary efficacy will be any reduction in PVC burden based on ambulatory heart monitors.

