4.2 Noninvasive Electrical Imaging

The method of electrocardiographic imaging (ECGI) is described in Section 1.5 above. Graphically, it is illustrated below:

In brief, the patient undergoes a CT scan while wearing a “vest” of electrodes that record heart beats. The electrical information from the surface of the body can then be computed onto the patient-specific heart model to noninvasively display the characteristics of the imaged heartbeat. Useful information includes: where the beat begins, how it depolarizes the heart, which parts of the heart have abnormal signals from previous heart attacks or scar. Fitting the vest of electrodes on the patient, obtaining electrical signals, and performing the CT scan is generally completed in under 30 minutes.

In this study, prior to treatment, patients will undergo ECGI during a noninvasive-programmed stimulation (called NIPS) procedure. A NIPS procedure is a commonly performed procedure in the cardiac electrophysiology lab. The patient receives light IV sedation for the procedure, and vital signs are monitored closely. Communication with the patient’s ICD is established, and the ICD is used to intentionally induce ventricular tachycardia through basic pacing maneuvers. Once the VT is induced, a 12-lead ECG and 256-lead ECGI are obtained (less than 10 seconds). The ICD is then again used to pace-terminate the VT (less than 10 seconds).

In this study, the NIPS will be performed in a standardized fashion. In the fasting state, single, double, and then triple extrastimuli will be delivered to refractoriness at drive trains of 600 and 400 ms, via the right ventricular ICD lead. Results from

the NIPS will yield electrical information (ECG and ECGI) that guides targeting of the noninvasive ablation to the areas of origin of the ventricular arrhythmias.

Despite the perceived risk of intentionally inducing a potentially life-threatening arrhythmia, NIPS is considered a rather low-risk procedure in the EP lab. Common risks include:

- Hypotension or adverse reaction to IV sedation (usually propofol);
- Induction of an arrhythmia that cannot be terminated by pacing, requiring external cardioversion/defibrillation or use of the ICD is necessary to restore regular rhythm

Contraindications for NIPS include:

- Because of the possibility for cardioversion/defibrillation, the most common contraindication for NIPS is the presence of atrial fibrillation in a patient that cannot receive anticoagulation

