11.2 Sample Size Justification

A total of 19 patients will be enrolled, which provides an optimal balance between assuring a high likelihood of safety (Phase I) with a preliminary assessment of efficacy (Phase II).

For the phase I component, the baseline rate of SAEs for catheter ablation is assumed to be 10-15%. Given the population being studied and a reasonable expectation that patients may be at a higher than typical risk of toxicity from any salvage therapy, we assume that SAE rates up to 20% would be clinically acceptable. Having said that, given that this is a totally noninvasive technique, it may well be that rates of toxicity are lower than that expected with catheter ablation. After exploring patient ranges from 15-25 patients, it was determined that 19 patients would provide a 75.4% power to detect an SAE rate about 20% (range, 5%-20%, $\alpha = 0.0829$).

For the phase II component, while some single institution series report much higher success rates, the baseline efficacy rate of catheter ablation in prospective trials ranges from 50-65%. As this is a salvage therapy in a high risk population, we assume that efficacy rates as low as 40% would be clinically acceptable. Using the 19 patient sample determined above, it was determined that 19 patients would provide 81.5% power to determine that ENCORE is not worse than 40% effective for the treatment of VT (range, 40-65%, $\alpha = 0.0885$).

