11.3 Analytic Plan for Primary Objectives

SAEs defined by CTCAE v4.0 criteria within 90 days of ENCORE that are possibly/probably/definitely related to study treatment will be recorded. ENCORE therapy will be deemed safe if the rate of SAEs is $\leq 20\%$. An additional early stopping rule dictates that if 5 or more out of the first 10 patients develop ENCORE related SAEs, the trial will be halted.

The number of ICD therapies delivered in the 6 month periods preceding and following ENCORE therapy will be recorded for each patient by interrogation of the ICD. ENCORE therapy will be deemed efficacious if there is a reduction in ICD therapies before and after treatment. The proportion of patients with efficacious ENCORE therapy will be calculated, with the intent of demonstrating at least 40% efficacy.

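### A serious event during the pre-treatment VT induction (NIPS) is, on the natural reading, left out of the safety rate, although the catheter-ablation benchmark covers locating the circuit as well as ablating it

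*Combined protocol and SAP*

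**What the plan says.** **Window and attribution.** Section 5.8: "Adverse events captured in the CRFs will be tracked for 12 months following SBRT", and "reportable adverse events are grade 3, 4, or 5 toxicities that did not predate SBRT" and are at least possibly attributable to treatment. Section 11.3 counts SAEs "within 90 days of ENCORE that are possibly/probably/definitely related to study treatment". Section 2.1 uses ENCORE as the short name for the radiotherapy itself: "Demonstrate acute (≤ 90 days) safety of noninvasive stereotactic cardiac ablation radiotherapy (ENCORE". Section 5.2 ties a treatment-related SAE to protocol treatment and does not mention protocol procedures.

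**Forms and denominator.** Toxicity Forms are due at 6 weeks, 3 months and 6 months after SBRT (8.0). The calendar (7.0) marks adverse event assessment from the Baseline column, but 8.0 lists no Toxicity Form before SBRT. Section 4.5 names as evaluable the patients who complete the full SBRT dose.

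**NIPS.** It is marked only at Baseline, ahead of the treatment column (7.0). Under light IV sedation "the ICD is used to intentionally induce ventricular tachycardia through basic pacing maneuvers", and the results guide targeting. Listed risks include hypotension, sedation reactions and "Induction of an arrhythmia that cannot be terminated by pacing, requiring external cardioversion/defibrillation" or use of the ICD (4.2).

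**Benchmark.** The 20% limit in 2.1 and 9.0 is based on published data for catheter VT-ablation procedures, and in 11.2 "the baseline rate of SAEs for catheter ablation is assumed to be 10-15" percent. Section 1.2 describes that procedure as finding the critical parts of the circuit and then ablating them.

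**The concern.** Like catheter ablation, the ENCORE pathway has a step that locates the circuit and a step that destroys it. For catheter ablation both fall within one procedure, so its complication rate covers both. For ENCORE the locating step that carries procedural risk comes before SBRT, and the text as written counts from SBRT onward.

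A patient seriously harmed during NIPS who still received SBRT would stay in the denominator with the event uncounted. A patient harmed so that SBRT was not given would drop out entirely. Both omissions lower the reported rate. At stake is whether the figure set beside the catheter-ablation rate describes the whole pathway or only its second half, and whether that question is settled before an event occurs.

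**Working it through.** **1. The plan's own figures.** Exact binomial, n = 19, safe if at most 1 SAE:
- P(X ≤ 1 | 0.20) = 0.0829, the stated alpha.
- P(X ≤ 1 | 0.05) = 0.7547, against a stated power of 75.4%.
- Stopping rule: P(X ≥ 5 | n = 10, 0.20) = 0.0328, below 0.05 as stated.

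These reproduce, so the point concerns which events are counted and not the arithmetic. The 20% criterion in 11.3 would pass up to 3/19 (15.8%), since 4/19 is 21.1%. Both cutoffs are shown below.

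**2. Is the benchmark a whole-procedure rate?** The complications listed in 1.2 are death 3%, stroke/TIA 1-2%, perforation 1-2%, heart block 1.6%, effusion/tamponade 1%, worsening heart failure/shock 1-2%, uncontrollable VT 1% and sepsis below 1%.
- Low end: 3 + 1 + 1 + 1.6 + 1 + 1 + 1 + 0 = 9.6%.
- High end: 3 + 2 + 2 + 1.6 + 1 + 2 + 1 + 1 = 13.6%.

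The sum ignores patients with more than one event. It agrees roughly with the 10-15% in 11.2, which fits a rate for the procedure as a whole.

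**3. Size of the NIPS gap.** The documents give no NIPS SAE rate, so q per patient is assumed, independent of SBRT events.
- (a) Chance of at least one NIPS SAE in 19 patients: 1 − (1 − q)^19.
- (b) Whole-pathway rate if SBRT alone carries 5%: 1 − 0.95(1 − q), with the chance of passing each cutoff.
- (c) If the whole-pathway rate is truly 20%, the SBRT-only rate is 1 − 0.80/(1 − q), with the chance of passing when only post-SBRT events are counted.

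| q | (a) | (b) rate | (b) P(≤1) | (b) P(≤3) | (c) rate | (c) P(≤1) | (c) P(≤3) |
|---|---|---|---|---|---|---|---|
| 0 | 0 | 5.0% | 75.5% | 98.7% | 20.0% | 8.3% | 45.5% |
| 1% | 17.4% | 5.95% | 68.7% | 97.6% | 19.2% | 9.6% | 49.1% |
| 2% | 31.9% | 6.9% | 61.9% | 96.2% | 18.4% | 11.2% | 52.8% |
| 5% | 62.3% | 9.75% | 43.5% | 89.3% | 15.8% | 17.4% | 64.8% |

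One patient is 1/19 = 5.3 percentage points.

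**4. Baseline MRI.** Section 4.1.1 cites 1 clinical event in 1,500 scans. Over 19 baseline scans: 1 − (1 − 1/1500)^19 = 1.3%. The day-3 scan falls inside the 90-day window and the 3-month scan at about its edge, so the start of the window does not exclude them.

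**5. Halting rule, side by side.** Section 11.1 halts if 5 or more of the first 10 patients have an SAE, with no condition on relatedness or timing. Sections 9.0 and 11.3 count ENCORE-related SAEs. A serious NIPS event would count under 11.1 and, on the natural reading, not under 9.0 or 11.3.

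**The case against.** A treatment-attributed endpoint is a legitimate choice for a phase I radiotherapy objective. That stands, and it is why the primary endpoint should stay as it is.

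Section 5.8 defines reportable events and is not the endpoint. Sections 2.1, 9.0 and 11.3 do not say explicitly when the window opens, and the Figure 3 caption, headed as the ENCORE procedure, includes MRI and mapping during VT. A broader reading of ENCORE is therefore possible. Exclusion is the natural reading, not a stated rule.

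NIPS risk may be small. Section 4.2 calls it rather low-risk, and a rescued arrhythmia is an SAE under 5.2 only if it is grade 3 or higher with hospitalization, or grade 4-5. The 1-5% range is pure assumption.

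Nor would such events be invisible. Adverse events are assessed at baseline, unanticipated problems arising from research procedures go to the IRB (5.3, 5.7), and the DSMC reviews toxicities (10.0). But a risk listed in the protocol may not qualify as unexpected, and none of these routes feeds the safety rate.

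Three stronger readings are tempting and are not supported:
- *That ICD-MRI adds materially to the gap.* MRI may be declined or withheld for listed reasons, baseline imaging may be waived if done within one year (4.1, 4.1.1), two of the three scans follow SBRT, and the cited event rate is very low.
- *That NIPS events cannot reach the halting rule.* The wording of 11.1 would admit them.
- *That the comparison with catheter ablation is biased overall in ENCORE's favour.* Omitting NIPS events does lower ENCORE's rate. But 20% is a ceiling of acceptability set above 10-15%, with no formal comparison, and 1.2 gives no time window for the catheter complications. Ninety days of counting for ENCORE could work the other way.

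**Conclusion.** The point holds as a cheap improvement, limited mainly to NIPS. Read naturally, 2.1, 4.5, 5.2, 5.8, 8.0 and 11.3 together keep a serious NIPS event out of the numerator and, if SBRT is not then given, the patient out of the denominator. The benchmark behind the 20% limit covers locating the circuit.

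The size rests on an assumed NIPS SAE rate, for which the documents give no figure. At 1%, 2% or 5%, the chance of at least one uncounted event in 19 patients is 17%, 32% or 62%. The effect on the conclusion depends on the cutoff. With SBRT alone at 5%, counting NIPS events lowers the chance of at most 3/19 from 98.7% to between 97.6% and 89.3%, but lowers the chance of at most 1/19 from 75.5% to between 68.7% and 43.5%.

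The documents do not show that the primary endpoint is invalid or that any stated figure is wrong.

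**What to change.** - Keep the SBRT-attributed SAE rate as the primary safety endpoint.
- In 5.8 and 11.3, say explicitly whether SAEs before SBRT count toward it. Record SAEs related to protocol procedures from the first study procedure, in all enrolled patients whether or not SBRT is delivered.
- In 8.0, add a Toxicity Form due before SBRT, so that the baseline assessment already in 7.0 has somewhere to be recorded.
- In 11.3, report a whole-pathway SAE rate (first study procedure to day 90 after SBRT, denominator all enrolled patients who start a study procedure) beside the SBRT-only rate. Use the whole-pathway rate when results are set against the catheter-ablation figures.
- Reconcile 11.1 with 9.0 and 11.3 on which SAEs count toward halting.

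The cost is one extra form, a second denominator and a reported SAE rate that may be slightly higher. No added visit or patient is needed.

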6.0 CORRELATIVE STUDIES

Quality of life (QOL) will be measured at baseline, 6 weeks, 6 months, and 12 months post completion of ENCORE, using the SF-36 questionnaire. Changes between baseline and each time point, as well as changes between time points, will be measured.

ECGI will be obtained at baseline, 3 and 12 months after ENCORE treatment. Comparisons will be made of the putative purely ECGI-derived target volume vs. clinically-derived target volume on protocol, as well as comparison of post-ENCORE month ECGI with baseline ECGI with correlation of changes on ECGI with ENCORE dose distribution

Delayed contrast enhanced cardiac MRI (DE cMRI) will be obtained at baseline, 1-3 days and 3 months after ENCORE treatment. While initial MRI will help identify anatomic scar to target therapy, follow up DE cMRI will be used to identify tissue edema and myocardial ablation, as well as assess for cardiac and extracardiac complications.

Blood work will be drawn at baseline, 3 days and 3 months after ENCORE treatment. Specific markers will be used to assess for biochemical evidence of myocyte injury (troponin), endothelial

injury/activation (E-selectin), fibrosis (galectin-3), and prothrombotic effects (von Willibrand factor).

In patients who die or undergo a heart transplant, clinical reports will be reviewed and abstracted of any pathologic, histologic, or autopsy analysis. Additionally, clinically processed tissue submitted to the Department of Pathology may be requested for additional analysis for research purposes, including, but not limited to, assessment of the location and degree of baseline injury outside the radiotherapy target and evidence of on and off-target injury from radiotherapy.

